### **A. Sample Size and Power**

This was a system-wide initiative with the intention that all eligible adolescent patients receive the reminder/recall. Therefore, power calculations were not done. We estimate about 18,600 MCHS adolescent patients aged 12-17 years, of whom, 25% or about 4,650 have completed the COVID-19 primary series and may be due for the booster dose.

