## II. BACKGROUND

To increase protection against SARS-CoV-2 infection, a single COVID-19 booster dose was recommended in the United States for adolescents aged 16-17 years in December 2021 and 12-15 years in January 2022. Uptake of the first COVID-19 booster dose among children and adolescents has been suboptimal. As of August 2022, booster dose coverage among adolescents aged 12 through 17 years was 33% compared to 70% among adults aged  $\geq 65$  years.

Centralized reminder and recall systems have been shown to be a cost-effective strategy to increase vaccination rates. Reminder and recall at Marshfield Clinic Health System (MCHS) are centralized and target young children aged 18-23 months and adolescents aged 12 years. In accordance with CDC and MCHS vaccination recommendations, COVID-19 vaccine was added to the reminder/recall letters for 12-year olds due for tetanus, diphtheria, and acellular pertussis vaccine (Tdap), meningococcal conjugate vaccine (MenACWY), or human papillomavirus (HPV) vaccine in the summer of 2021.

Beginning January 2022, individuals aged 12 and older who have completed the primary series were eligible to receive COVID-19 boosters. We propose to assess the efficacy of a one-time reminder/recall targeting adolescents aged 12-17 years who are eligible, but have not yet received the booster vaccine.

[figure not shown]
The intervention will leverage the existing MCHS's centralized reminder/recall system and process for enrolling patients for text and email communication regarding appointments and healthcare updates. The proposed intervention is a component of a larger project funded by the Centers for Disease Control and Prevention (CDC) to understand and address determinants of rural-urban differences in vaccine uptake among adolescents in the upper Midwest (NCT05148559).

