### A. Inclusion Criteria

- Marshfield Clinic Health System patient aged 12-17 years with at least one preventive visit or two evaluation & management visits with a MCHS provider in the last 36 months
- Due for at COVID-19 booster dose (completed the COVID-19 primary series and it has been  $\geq 5$  months after the second dose)

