## **B. Exclusion Criteria**

- Primary care provider is not affiliated with MCHS
- Opted out of MCHS's centralized vaccine reminder notifications
- Received COVID-19 vaccine off label
- Missing or invalid contact information
- Deceased

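### Does the estimate of about 4,650 adolescents overstate the number randomized and the precision of the comparison?

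*Protocol*

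**What the plan says.** Protocol section VIII.A, Sample Size and Power, starts from the patient base, "We estimate about 18,600 MCHS adolescent patients aged 12-17 years", and continues: "25% or about 4,650 have completed the COVID-19 primary series and may be due for the booster dose". Because the initiative is system-wide and every eligible patient is meant to get the reminder, the section concludes: "Therefore, power calculations were not done".

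The group to be randomized is defined elsewhere. Section II aims the reminder at adolescents "who are eligible, but have not yet received the booster vaccine". The Inclusion Criteria ask for a completed series with at least 5 months since the second dose, and for a patient "with at least one preventive visit or two evaluation & management visits with a MCHS provider in the last 36 months". The Exclusion Criteria remove anyone for whom "Primary care provider is not affiliated with MCHS" applies, along with opt-outs, off-label recipients, patients with missing or invalid contact details, and the deceased.

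Under Randomization (VI.A), every patient eligible at data extraction is allocated 1:1. Section VI says that usual care gets the reminder after the 90-day evaluation period. Section VIII plans an absolute difference in booster receipt with confidence intervals.

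**The concern.** The only number a reader can use to picture the trial's size is 4,650, or 2,325 per arm. Yet the estimate shows no deduction for adolescents already boosted, those not yet 5 months past dose 2, or those removed by the exclusions. The first group is unlikely to be empty. Section II dates the booster recommendation to December 2021 for ages 16-17 and January 2022 for ages 12-15, both before the planned Spring 2022 intervention. The same section reports that nationally "booster dose coverage among adolescents aged 12 through 17 years was 33" percent.

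The reason for giving no power figure also looks weak. That everyone eventually gets the reminder explains why the number is not chosen, but the primary comparison still withholds it from half the patients for 90 days. If the real number is well below 4,650, the trial can detect only larger effects than a reader might suppose. A one-time reminder may have a small effect, so this could colour how a null result is read.

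**Working it through.** **1. The plan's own figure.** 18,600 × 0.25 = 4,650. It reproduces exactly, so there is no arithmetic error.

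**2. What it counts.** The 25% is attached to completing the series; being due is only a possibility. It could be read as 25% meeting both conditions, but that is the less natural reading. As a completer count, it can only fall when the remaining criteria are applied. One deduction is uncertain: the Protocol does not say how the 18,600 patients were defined, so the visit criterion may already be reflected in that base.

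**3. Can the 33% give a corrected number?** Applied to all patients, 0.33 × 18,600 = 6,138, more than the 4,650 completers, so it cannot be a share of this patient base. That does not show that its denominator is completers. It shows that the national figure may not transfer to this population. It is also dated August 2022, after the planned intervention period, and no denominator is given. It can serve as an illustration only.

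**4. Illustrative sizes.** N = 4,650 × (1 − b) × (1 − e), where b is the share of completers already boosted or not yet due and e is the share failing other criteria. Both are assumptions.

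- b = 0.33, e = 0: 4,650 × 0.67 = 3,115.5, about 3,115
- b = 0.33, e = 0.20: 3,115.5 × 0.80 = 2,492
- b = 0.10, e = 0: 4,185
- b = 0.50, e = 0.30: 4,650 × 0.50 × 0.70 = 1,628

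Over b from 10% to 50% and e from 0% to 30%, N runs from about 4,185 down to 1,628. The documents do not narrow this.

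**5. What the size does to precision.** With n = N/2 per arm and an assumed control rate p = 0.10:

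- 95% half-width = 1.96 × √(2p(1 − p)/n). At N = 4,650 this is 1.96 × √(0.18/2,325) = 1.72 points.
- Detectable difference d at 80% power, two-sided 5%, solves d = (1.96 + 0.84) × √{[p(1 − p) + (p + d)(1 − p − d)]/n}.

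| N | Half-width (points) | Detectable difference (points) |
|---|---|---|
| 4,650 | 1.72 | 2.60 |
| 3,115 | 2.11 | 3.21 |
| 2,492 | 2.36 | 3.62 |
| 1,628 | 2.92 | 4.55 |

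Removing 33% widens the interval by √(1/0.67) = 1.22. Removing 65% (N = 1,628) widens it by √(1/0.35) = 1.69. With control rates from 5% to 20%, the half-width is 1.25 to 2.30 points at 4,650 and 2.12 to 3.89 points at 1,628.

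**6. Does any of this reach a result?** The number randomized is whatever extraction yields, and the confidence interval in section VIII is computed from those patients. No enrolment target, stopping point or decision rule uses 4,650.

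**The case for a change.** The best case for a change is that it costs two sentences. The label could say that 4,650 is an upper bound, and the expected interval half-width at the realistic size could replace the remark on power. The document cites material retrieved in September 2022, after the planned Spring 2022 period, so an actual extraction count should have been obtainable. The reason given for having no power figure also does not explain why the expected precision of the randomized comparison goes unstated.

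Part of this stands. The estimate is most naturally an upper bound, and an expected half-width would inform readers. But the rationale is not contradicted by the design: the reminder is delayed for usual care, not denied, and when all eligible patients are randomized there is no sample size to choose. Expected precision at a fixed size is something a statistical analysis plan, not shown here, could hold. Putting in a replacement range would do harm. Assuming 20% to 40% already boosted gives 3,720 to 2,790, but that is before the 5-month interval and the other exclusions are counted, so calling it the post-exclusion number would repeat the fault.

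**Conclusion.** No change is needed. The stated figure is arithmetically right and hedged, and it is not presented as the number randomized. The Protocol claims no power or precision, so none is overstated. A reader who derives precision from 4,650 would be too optimistic: by a factor of about 1.22 if 33% of completers were already boosted, and by up to about 1.69 under the heaviest deductions considered. Those factors rest on assumed deductions, and the widths in points also rest on an assumed control rate. The documents fix neither.

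A null result would be judged by its reported confidence interval, which reflects the patients actually randomized; a planning estimate cannot narrow it. The missing detail is the count eligible at extraction, which analysts will have as soon as randomization is run and would ordinarily report. Relabelling the estimate beforehand would change no analysis, decision or conclusion.

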## **IX. HUMAN SUBJECTS CONSIDERATIONS**

This is a quality improvement initiative aimed at measuring the impact of a focused intervention to improve adolescent vaccination rates. Potential risks are limited to the possibility that participants' identifying information would be inadvertently disclosed. We do not anticipate any major risk to participants hence, a waiver of informed consent and HIPAA authorization have been requested and approved by the MCHS Institutional Review Board.

**XI. APPENDIX**

**Intervention mailed letter/email**

**Give your child's COVID-19 vaccination protection a boost.**

Dear Parent or Guardian:

This is a reminder that <<child's name>> is due for their COVID-19 booster dose.

Everyone ages 12 years and older is recommended to get a booster dose for the best protection against COVID-19 and circulating variants. Preteens who are up to date with their COVID-19 vaccinations and symptom free do not have to miss school or other activities because of quarantine after close contact.

Please contact Marshfield Children's at [contact] to schedule an appointment today. To self-schedule online, visit <https://www.marshfieldclinic.org/covidvaccine>.

If <<child's name>> received COVID-19 vaccine or other vaccines from another provider, please let us know so we can update our records. If you need help paying for vaccinations, our Patient Assistance Center can help. Please call them at [name].

Thank you for allowing us to care for <<child's name>>.

Marshfield Children's

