## **VI. INTERVENTION**

The intervention (reminder/recall) consisted of a one-time booster dose reminder sent to parents using their specified preferred communication method (postal mail, email, or text). The default preferred communication method will be postal mail (letter) if text or email is not specified in the electronic health record. The reminder/recall message will differ for those who will receive text versus letter or email, due to restrictions on privacy and length of text messages ([APPENDIX](#)). The usual care group will not receive the reminder/recall until after the 90-day evaluation period. All persons in the usual care group will receive the reminder/recall via mailed letter.

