### **A. Randomization**

Eligible adolescents will be stratified based on communication method and rurality (using home address). Each patient who is eligible at the time of data extraction/randomization will be assigned a random number, which will be used to facilitate stratified random sampling. Within each strata, the random number will be used to assign patients to intervention (reminder/recall sent via postal mail, text or email) or usual care (no reminder/recall) arm in a 1:1 ratio.

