## **VII. OUTCOME MEASURES**

### **A. Primary Endpoint**

The primary endpoint will be documentation of receipt of a COVID-19 booster dose during the 90 days after randomization (90-day evaluation period).

Receipt of COVID-19 booster dose will be obtained from data available from the MCHS electronic health data, which includes a local vaccination registry that exchanges vaccination data from the state immunization registry.

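### Do the reminder letter's reference to preteens and the deferred mailing to everyone in usual care call for a change to the plan?

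*Protocol*

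**What the plan says.** The eligible population is stated in Protocol Section IV.A: a "Marshfield Clinic Health System patient aged 12-17 years" who is due for a booster. The intervention is a single reminder. Section VI makes the letter the fallback channel: "The default preferred communication method will be postal mail (letter) if text or email is not specified". Email uses the same text as the letter; text messages use a shorter one.

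The letter/email template in Section XI names the child as due and then says "Everyone ages 12 years and older is recommended to get a booster dose". The next sentence narrows its audience: "Preteens who are up to date with their COVID-19 vaccinations and symptom free do not have to miss school or other activities" on account of quarantine. The text message has no such sentence.

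For the control arm, Section VI holds the reminder back until the 90-day evaluation period is over and adds that "All persons in the usual care group will receive the reminder/recall via mailed letter". Section VI.A fixes eligibility once: "Each patient who is eligible at the time of data extraction/randomization" receives a random number. Section VIII.A describes a system-wide initiative "with the intention that all eligible adolescent patients receive the reminder/recall". The endpoint in Section VII.A comes from the health system's electronic data, "which includes a local vaccination registry that exchanges vaccination data from the state immunization registry".

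**The concern.** There are two separate points.

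**The age wording.** The letter is the tested intervention wherever contact is by mail or email, and mail is the default. The quarantine sentence gives the letter's one everyday reason to act. On ordinary usage a preteen is at most 12, so the sentence passes over ages 13 to 17, which make up most of the enrolled range. If that weakens the message for older adolescents, the trial could show a smaller effect than a letter worded for the whole range would have produced.

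**The deferred mailing.** Read literally, everyone in usual care is mailed, including adolescents whose booster within the 90 days has just been counted as an endpoint event. If the Appendix template is reused, their parents are told that a dose is due when the health system's own records show it was given. At stake is the accuracy of a communication to families.

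**Working it through.** **The plan's own figure.** Section VIII.A takes about 18,600 adolescents, of whom 25% have completed the primary series: 0.25 × 18,600 = 4,650, as stated. With 1:1 allocation (Section VI.A), 4,650 / 2 = 2,325 per arm. The 4,650 are patients who may be due, so the number randomised could be smaller.

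**How many families the age wording could touch.** Ages 13 to 17 are 5 of the 6 single-year ages, and 5/6 = 83% if ages are evenly spread. The age spread is not given. If 12-year-olds are 25% or 10% of those enrolled, the share aged 13 to 17 is 75% or 90%. The share contacted by letter or email is not given either, so I take 50%, 75% and 100%.

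| Share aged 13–17 (assumed) | Letter/email share (assumed) | Intervention-arm families |
|---|---|---|
| 75% | 50% | 2,325 × 0.75 × 0.50 ≈ 872 |
| 83% | 50% | 2,325 × 5/6 × 0.50 ≈ 969 |
| 83% | 75% | 2,325 × 5/6 × 0.75 ≈ 1,453 |
| 83% | 100% | 2,325 × 5/6 ≈ 1,938 |
| 90% | 100% | 2,325 × 0.90 ≈ 2,093 |

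The answer moves more than twofold with inputs that the documents do not supply.

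**How many controls could be mailed although boosted.** Booster uptake in usual care is not given. At 2%, 5%, 10% and 20% (assumed), 2,325 times the rate gives about 47, 116, 233 and 465. Nothing in the documents makes 20% a ceiling.

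**What these counts mean for the comparison.**

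1. *Age wording.* Randomisation is stratified by communication method. Within the mail and email strata the contrast is therefore the letter as written against no reminder; in the text stratum it is the text message against no reminder. A clumsy sentence is part of the treatment. It may make the treatment weaker, but it does not distort the estimate of what that treatment did. The documents give nothing from which to put a number on any loss of effect.
2. *What still reaches ages 13 to 17.* The letter names the child, says the dose is due, recommends it for everyone aged 12 or over, and gives a telephone and an online route to book. One supporting sentence is misaddressed; the call to act is not.
3. *Deferred mailing.* The endpoint counts doses within 90 days of randomisation, and the control mailing comes after that. A letter sent then cannot cause a dose inside the window, so it contributes nothing to the difference between arms.

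**The passages on the deferred mailing, side by side.** The sentence in Section VI follows a description of three channels and tells the reader that controls are mailed whatever channel their parents prefer. It can be read as settling the channel, not as overriding eligibility. Section II describes the target as adolescents who qualify and are still without the booster, and Section VIII.A states the aim for eligible patients. Section II also says that the reminder runs on an existing centralised recall system. Read together, these passages imply a list limited to those still due. What is missing is an explicit statement that the list is refreshed, which is operational detail.

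**The case for a change.** The strongest case for acting is that both mismatches can be verified, the letter is the intervention itself, and correction costs almost nothing: one edit to a template and one repeat of an extraction query. The quarantine sentence disagrees in scope with the sentence before it and with the inclusion criteria, and the protocol gives no reason for limiting it to preteens. Section II says that the existing adolescent recall is aimed at 12-year-olds, so the word may have been carried over from that letter; this is an inference. On the mailing, the health system will know at day 90 which controls were boosted. The letter's request that families report doses given by another provider does not help where the dose is already on record.

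The textual observations stand. Three things limit what follows from them.

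- A low cost does not make a gain. Neither correction alters the endpoint, the randomisation or the analysis, and no improvement in the estimate can be shown.
- Whether the quarantine statement holds for all of ages 12 to 17 depends on guidance outside the documents. Only the sponsor could confirm that the wording may be widened.
- The opportunity has probably gone. Section V places the intervention in Spring 2022, but Section II cites coverage as of August 2022, a reference was retrieved in September 2022, and Sections VI and VIII.A slip into the past tense. The reminders had very likely been sent, and the control mailing may have been due or done.

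**Conclusion.** No change to the plan follows. The preteen wording is a clerical slip in one sentence of the letter and email. The silence on refreshing the control mailing list is a gap that the staff running the recall would fill sensibly, in line with the aim in Section VIII.A.

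The effect on the primary comparison is nil for the deferred mailing, because it falls after the 90-day window. For the wording there is no bias, because the trial estimates the effect of the message as sent; any dilution of that effect cannot be quantified from the documents. The family counts (about 872 to 2,093, and about 47 to 465) rest wholly on assumed age spread, channel share and control uptake, and on all 4,650 being randomised. They show how many letters might carry the wording or go out unnecessarily, and do not measure harm to the trial.

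A reader interpreting the result should know that the letter was tested as it appears in the Appendix. Printing the template with the report, as the protocol already does, is enough for that.

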**Intervention text message**

From Marshfield Children's: Everyone ages 12 years and older is recommended to get a booster dose for the best protection against COVID-19 and circulating variants. Please call [contact] to schedule a booster appointment today. To self-schedule online, visit <https://www.marshfieldclinic.org/covidvaccine>. Please do not reply.
